6.1 Sample Size and Power Determination

We estimate enrollment of roughly 30-40 patients. This is a pilot study since there has been no similar attempt at using and validating awake endoscopy for implant activation. Sample size and power calculations for paired t-test indicate that ~30 subjects would yield a study that is powered to detect a 50% effect size (using a standard $\alpha=0.05$, $\beta=0.2$). Additional subjects would enable detection of a smaller effect size.

6.2 Statistical Methods

Analysis of all outcomes will be performed at the completion of the study. In the analysis of the primary outcome of interest, paired t-tests will be used to compare differences in AHI and ODI using the test Inspire device configuration and the standard device configuration. Paired t-tests will also be used to analyze whether significant differences in airway size exist using different device configurations: namely, the “test” configuration that has the largest airway size compared to the standard device configuration. A Pearson correlation test will be used to determine whether changes in airway size using standard and test configurations correlate with changes AHI and changes in ODI.

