Data and Safety Monitoring Plan	PI will be responsible for monitoring the data quality and the ongoing safety of subjects.

CONFIDENTIAL

Background and Study Rationale

1 Introduction

The Inspire Upper Airway Stimulation (UAS) system is an FDA-approved, commercially available, innovative surgical solution for patients with moderate-to-severe obstructive sleep apnea (OSA) that have failed continuous positive airway pressure (CPAP) therapy. It is a surgically-implanted device that is implanted in anesthetized patients using three incisions: a sensing lead that senses inspiration is placed in the lateral intercostal muscles in the low lateral chest, a pacemaker device is placed in the upper chest wall, and a stimulation lead is placed around the hypoglossal nerve in the neck for stimulation of tongue movement. This system is designed to push the tongue forward during inspiration to keep the upper airway open in patients who have tissue collapse causing obstructive sleep apnea. The Inspire device was FDA-approved for the treatment of moderate-to-severe OSA in 2014 and has been implanted in over 1,000 patients to date. Patients undergo outpatient surgery under general anesthesia for implantation then return to see their surgeon at 1 month postoperatively for device activation, which is performed in the awake patient. Current standard-of-care is to activate patients' devices using the "standard configuration" which is the +-+ electrode configuration. This "standard configuration" was determined by the Inspire Corporation, though there are many other possible configurations of the 3-electrode stimulation lead. These different configurations (e.g., +0+, +-+, etc) result in different stimulatory patterns of the hypoglossal nerve and different changes in upper airway architecture, however it is unknown how these changes differ among patients. In the current standard-of-care algorithm, after device activation, patients proceed to outpatient sleep study to titrate their device and assess their response to therapy. While most patients achieve therapeutic benefit from this initial standard setting, a subset of patients for which this is initial configuration is unsuccessful later undergoes awake endoscopy where the surgeon may examine the airway during stimulation with multiple other implant settings. Based on this exam, the surgeon then selects another setting to be tested during a repeat sleep study. **This subset of patients experiences a delay in delivery of effective therapy for OSA. Furthermore, it is unknown whether the patients who are successfully treated with the initial device setting are being optimally treated.** It is possible that these successfully treated patients could have an even greater response with reduction in OSA symptoms and burden of disease if they were to use a different implant setting. The goal of this study is to evaluate the efficacy of awake endoscopy during implant activation. We hypothesize that awake endoscopy can be used during the initial postoperative visit to identify an "optimal" implant configuration based on greatest change in airway size, and that changes in airway size will correlate with an improvement in measures of obstructive sleep apnea on polysomnography.

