The aim of this study is to examine a new method of device configuration for the Inspire upper airway stimulator. First, we will attempt to determine optimal configuration by quantifying changes in upper airway size with different implant configurations using awake nasal endoscopy. The configuration/voltage that results in the greatest increase in upper airway size and is tolerated by the patient will be selected. Patients will then undergo a sleep study so that increased airway size may be correlated with changes in sleep study parameters including AHI and oxygen desaturation index (ODI). Airway size and sleep study parameters using the standard device configuration (++)/voltage will be compared to airway size and sleep study parameters using the test, or “optimal,” configuration/voltage to determine the usefulness of awake endoscopy in activation of the Inspire device.

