3.3 Study Measures

Awake endoscopy will be performed during Visit 1 during which airway size will be video recorded at rest with implant off and with a standardized sequence of implant configurations that were determined by Inspire Corporation during pre-market testing including +++, ---, o-o, -o-, and -+-+. These settings will be tested to determine the voltage at which patients sense tongue movement (sensation threshold) and the voltage at which the tongue is visualized protruding from rest past the teeth (functional threshold). The different electrode configurations will then be tested at various voltages above the subject’s measured functional thresholds.

Measurements of cross-sectional, anterior-to-posterior, and lateral airway size in the retropalatal and retroglossal regions will be taken from recorded endoscopic exams using the image analysis program Amira by Visage Imaging (Richmond, Victoria, Australia). Measurements will take place between Visits 1 and 2. Standard AHI and ODI measurements will take place during in-lab sleep study (Visit 2). Efficacy of awake endoscopy to determine optimal device configuration will be assessed by comparing cross-sectional airway size (retropalatal and retroglossal), AHI and ODI with the standard device configuration compared to airway size, AHI and ODI with the test configuration. In patients for whom the standard configuration (+++) results in greatest airway size, this will be the sole configuration tested during sleep study, and identical values for airway size, AHI, and ODI will be used in analysis comparing the standard configuration with the “test” configuration.

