5.2 Study Intervention

5.2.1 Visit 1: Otolaryngology Clinic for Awake Endoscopy

- Informed consent
- Vital signs: HR, RR, BP, SpO₂, BMI
- Targeted Head and Neck Physical Exam
 - Tongue size, lateral peritonsilar narrowing, palate shape, Modified Mallampati score
- Recorded exam of awake endoscopy at rest and with standardized configurations detailed in section 3.3 (Attachment 1)
 - Measurement and analysis of airway size to be completed by single co-investigator between Visits 1 and 2. Configuration resulting in greatest airway size will be used as test configuration during Visit 2 sleep study.

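### The airway-size t-test in 6.2 compares the configuration chosen for its largest reading with the standard on the same readings, so on the selecting measure a small p-value does not show that configurations differ

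*Combined protocol and SAP*

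**What the plan says.** - **The test.** Section 6.2: "Paired t-tests will also be used to analyze whether significant differences in airway size exist using different device configurations". It then specifies the contrast: the "configuration that has the largest airway size compared to the standard device configuration".
- **The selection.** Section 5.2.1: "Configuration resulting in greatest airway size will be used as test configuration during Visit 2 sleep study". Section 2 adds tolerability: "The configuration/voltage that results in the greatest increase in upper airway size and is tolerated by the patient will be selected".
- **The candidates.** Section 3.3 lists five configurations, and the standard as printed there is one of them. Several voltages are recorded: "The different electrode configurations will then be tested at various voltages above the" subject's functional threshold.
- **When the standard wins.** Section 3.3: "identical values for airway size, AHI, and ODI will be used in analysis comparing the standard configuration" with the test one.
- **The readings.** Sections 3 and 5.2.1 describe one Visit 1 recording, measured by one blinded member of the team before Visit 2. No second recording and no adjustment for selection is described.
- **The role.** Airway change is a secondary endpoint (3.4.2). Section 3.3 also says efficacy is assessed by "comparing cross-sectional airway size (retropalatal and retroglossal), AHI and ODI with the standard device configuration" against the test configuration. The efficacy rule in 3.4.1 and 5.5 uses AHI and ODI only.

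**The concern.** A paired t-test is calibrated for differences that average zero when nothing is going on. Here one side of each pair is the maximum of a set and the other side is a member of that set. On the measure that decided the maximum, the difference cannot be negative if the standard was eligible, and any reading error or moment-to-moment variation makes its mean positive. The p-value then mostly reflects the act of choosing.

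At stake is a reported significant airway gain that readers would take as evidence that configurations open the airway differently, with an effect estimate that is too large. Blinding to subject history (6.3) does not help, because taking a maximum needs no knowledge of the patient.

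**Working it through.** **1. The plan's own figure.** Section 6.1 gives about 30 subjects for a 50% effect size, which I read as 0.5 SD of the paired differences. The two-sided normal approximation is n = ((1.960 + 0.842)/0.5)² = 31.4, so 32, close to the plan's figure (an exact t calculation gives 34). No figure is given for the airway test. I use n = 30, with n = 40 as a check.

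**2. Sign of the difference.** For one patient, D = max(X₁,…,X₅) − X_standard. The standard is one of the five, so D ≥ 0, and D = 0 when the standard wins. Few positive values are needed for significance. Suppose 4 of 30 patients have D = 1 and the rest have 0. The mean is 4/30 = 0.133, the SD is √((4 − 16/30)/29) = 0.346, and t = 0.133/(0.346/√30) = 2.11, p = 0.043.

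**3. Truly equal configurations.** Let s be the error SD of one reading. It is not in the documents; rejection in this case does not depend on it. I assume independent normal errors.

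- The mean of D is the expected maximum of five standard normals, 1.163 s (simulated 1.162 s, with 20% exact zeros). The SD of D is 1.025 s, so a typical t is 1.162/(1.025/√30) = 6.2.
- Simulated rejection is 100% at n = 30 and at n = 40. With only two candidates it is 99.9% at n = 30.
- If the standard is truly *larger* than every alternative by 1, 1.5 or 2 s, the test still favours the selected configuration in 99.9%, 95% or 57% of trials.
- Control checks: with selection on one recording and testing on an independent one, rejection is 5.2%. With a configuration fixed in advance, it is 4.9%.

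**4. Real patient-level differences.** Let the true differences have SD τ (in units of s) and no average effect. The measured gain is 1.163·√(τ² + 1), the true gain is that value times τ²/(τ² + 1), and the artefact share is 1/(1 + τ²). Simulated gains:

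| τ | Measured gain (s) | True gain (s) | Artefact share |
|---|---|---|---|
| 0.5 | 1.30 | 0.26 | 1/1.25 = 80% |
| 1 | 1.65 | 0.82 | 1/2 = 50% |
| 2 | 2.61 | 2.09 | 1/5 = 20% |
| 4 | 4.81 | 4.52 | 1/17 = 6% |

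Rejection is 100% in every row, as it is with no differences at all, so the p-value cannot tell these cases apart.

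**5. What the documents leave open** (equal configurations, n = 30).

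- *Comparator reading.* With 2 or 3 voltages per configuration (an assumed number), the spurious gain is 0.98 or 0.89 s if the standard is taken at its own best reading, 1.37 or 1.49 s at one fixed voltage, and 0.82 or 0.67 s if voltages are averaged first. Rejection is 100% throughout.
- *Two regions selecting jointly, independent errors.* 16% of differences are negative and rejection is 98%.
- *Standard not tolerated in 10% or 30% of subjects.* 2% or 6% of differences are negative and rejection stays at about 100%.
- *A measure not used to select.* At error correlation 0, 0.3, 0.5 or 0.8 with the selecting measure, rejection is 5%, 31%, 74% or 99.8%.

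**The case against.** **The test may be nearly valid for some measures.** A reader might infer that the airway test will come out significant on every measure, whether or not any configuration enlarges the airway. The documents do not support that. Section 3.3 compares two regions, and neither 3.3 nor 5.2.1 says which region or combination defines the greatest airway. If one region selects and the other's error is uncorrelated with it, the test on the other region holds its 5% level. This objection stands and limits the claim to the selecting measure and those correlated with it.

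**The bias may be small.** Section 1 states that configurations change the airway differently and that "however it is unknown how these changes differ among patients". If readings are precise relative to those differences, the artefact is a few percent of the gain. That is fair: the documents allow neither a large nor a trivial bias to be asserted. It does not rescue the p-value, which is uninformative on the selecting measure in either case.

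**The secondary endpoint may be something else.** Section 3.4.2 can be read as change from the device-off recording for each configuration, which involves no selection. That stands. The fault lies in the 6.2 contrast, not necessarily in the endpoint.

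**The comparator is partly indicated.** Section 2 speaks of a standard configuration and voltage, and section 3 describes titration to tongue protrusion. This points to a standard activation voltage but does not say which recorded reading enters the analysis.

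**Little depends on it.** Section 6.1 calls this a pilot, and no decision rule uses the airway p-value. That holds, and it sets the weight of the point.

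**Conclusion.** The concern holds for the airway measure used to select. There the planned t-test rejects in about 100% of trials when configurations are truly equal (about 98% if two regions select jointly with independent errors), and the reported gain is too large by an amount that cannot be fixed from the documents. For other airway measures the effect ranges from none to almost as severe, depending on error correlation.

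A reader might go further and infer that the efficacy conclusion is compromised. It is not compromised by this route: AHI and ODI come from a separate sleep study, so choosing on airway readings does not by itself inflate those tests. This is a secondary-analysis fault that should be fixed.

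The figures assume independent normal reading errors of equal SD, five candidates, n = 30 and two-sided α = 0.05. The direction of the bias needs only that readings vary and that the standard is among the candidates.

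**What to change.** **Section 6.2.** Replace the test-versus-standard airway t-test with:

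> The airway gain of the selected configuration over the standard will be reported descriptively (absolute and percent), without a p-value, and labelled as subject to selection bias because the configuration was chosen on the same readings.

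**Sections 3.3 and 5.2.1.** Name the measure that defines the greatest airway (dimension, and region or combination). State which recorded reading of the standard is the analysis comparator.

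**Optional, only if a test of configuration differences is wanted.** Compare each subject's mean airway size per configuration with that under the standard, by Holm-adjusted paired t-tests, and name the readings that enter each mean. These test average configuration effects, not patient-specific gain. In simulations with no average effect but unequal patient-level spread (five configurations, three voltages assumed), the first Holm step rejected in 3.3% or 4.6% of trials.

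**Cost.** One sentence and two definitions, with no new visits or data. The airway gain loses its p-value. A valid test of patient-specific gain would need a second independent recording of each configuration, which would lengthen a visit scheduled at 30 minutes, so I would not make it the default.

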2.2 Secondary Objectives (if applicable)

- To determine optimal configuration/voltage of the Inspire upper airway stimulator by quantifying changes in upper airway size with multiple implant configurations
- To correlate change in airway size seen on awake endoscopy with outcomes of observed sleep study including AHI and ODI

3 Investigational Plan

Patients who are undergoing Inspire implantation by the principal investigator will be screened to determine whether they meet inclusion criteria and invited to participate in the study. All components of the study will be performed during visits that are scheduled as part of routine postoperative care; these visits will be modified to incorporate study activities. Written consent will be obtained at Visit 1. Subjects will present to clinic (Visit 1) for awake endoscopy during their regularly scheduled postoperative activation appointment. An aerosolized mixture of xylocaine and oxymetolazone (afrin) will be used as a numbing agent prior to awake endoscopy; this is routinely used for awake endoscopic exams in the ENT clinic. The surgeon will perform awake nasal endoscopy while a clinical assistant or nurse activates and configures the device using the Inspire remote control. Device voltage will be titrated to achieve tongue protrusion across the teeth, which is part of the standard method of activation. Endoscopic exam will be recorded and include visualization of baseline airway with device turned off and airway with multiple test configurations and voltages. At the end of this visit, devices will be set to the standard device configuration that is currently used in routine clinical practice (++) . Patients then routinely use their device at home for the following month. The recorded exam will be used by a single blinded member of

CONFIDENTIAL

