3.4 Study Endpoints

3.4.1 Primary Study Endpoint

The primary endpoint is to assess the efficacy of awake endoscopy in determining optimal implant configuration during implant activation. A decrease in AHI and ODI with test configuration compared to standard configuration will indicate that awake endoscopy is useful for identifying optimal implant configuration compared to the current method of activation without endoscopy.

CONFIDENTIAL

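### On the plain reading of 6.2, subjects with copied values sit at exactly (0,0) in the Pearson correlation, which can make it significant with no association among subjects whose setting changed

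*Combined protocol and SAP*

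**What the plan says.** The secondary objective in 2.2 is "To correlate change in airway size seen on awake endoscopy with outcomes of observed sleep study including AHI and ODI". Section 6.2 carries it out with a Pearson test of whether "changes in airway size using standard and test configurations correlate with changes AHI and changes in ODI". It names no subset, exclusion or sensitivity analysis.

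Two other rules decide what enters that test:

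- **Choice of test setting (5.2.1):** "Configuration resulting in greatest airway size will be used as test configuration during Visit 2 sleep study".
- **Subjects whose standard setting is already best (3.3):** "In patients for whom the standard configuration (+++) results in greatest airway size, this will be the sole configuration tested during sleep study". For them, "identical values for airway size, AHI, and ODI will be used in analysis comparing the standard configuration with the" test configuration.

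Section 3.4.1 states the expected direction: "A decrease in AHI and ODI with test configuration compared to standard configuration will indicate that awake endoscopy is useful". The documents do not say how many subjects are expected to have the standard setting as their best.

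**The concern.** Take change as test minus standard. A subject with copied values then has zero airway change and zero AHI and ODI change, although only one setting was recorded in the sleep study. Switchers (subjects whose test setting differs from the standard) have a positive change in whichever airway measure selected the setting, because it was selected for being largest.

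The scatter plot is therefore a spike at the origin and a cloud to its right. If the cloud's mean AHI change is not zero, the line from spike to cloud is itself a correlation. It says nothing about whether larger airway gains go with larger falls in AHI. Any airway measure, even one unrelated to AHI, would show it.

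The mean shift among switchers may be a real benefit of the test setting. It may also have other sources: 5.2.2 gives each setting half of one night with no stated order, and Section 3 allows voltage to be raised with either setting.

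The introduction hypothesises that airway change will correlate with improvement on polysomnography. A significant r would be read as evidence that airway size is a valid guide to configuration.

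**Working it through.** **Inputs from the documents**

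- Enrolment: "We estimate enrollment of roughly 30-40 patients" (6.1). I use the midpoint, 35.
- Effect size: "30 subjects would yield a study that is powered to detect a 50% effect size" (6.1), read as a standardised difference of 0.5, with alpha 0.05 and power 0.80.
- Copied values give (0,0) (3.3); the correlation has no exclusions (6.2).

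**Assumed, because the documents give no figure**

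- Share of switchers s (non-switchers f = 1 - s): 50% to 90%.
- Airway change among switchers: gamma, mean/SD 1.5.
- AHI change among switchers: normal, mean shift -0.3, -0.5 or -0.8 SD, independent of airway change. The true association among switchers is therefore zero.

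**The plan's own figure.** Section 6.1 sizes only the paired t-test. The normal approximation gives n = ((1.960 + 0.842)/0.5)^2 = 31.4, so 32, close to the stated 30 or so. The exact t calculation gives 34, and 30 subjects give 75.4% power. There is no figure for the Pearson test. I borrow 0.5 from here as the central AHI shift; applying it to switchers alone is my assumption.

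**Induced correlation.** Write each change as S x A (airway) and S x H (AHI), where S is 1 for switchers and 0 otherwise, and A and H are independent with means mA, mH and SDs sdA, sdH. Then:

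- covariance = s(1-s) mA mH
- variance of airway change = s sdA^2 + s(1-s) mA^2, and likewise for AHI
- so r = sign(mH) x f / sqrt[(CVa^2 + f)(CVh^2 + f)], where CV = SD/|mean| among switchers and mA is positive

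With CVa^2 = (1/1.5)^2 = 0.444 and CVh^2 = (1/0.5)^2 = 4, at f = 0.4: r = -0.4 / sqrt(0.844 x 4.4) = -0.4 / 1.928 = -0.21. This is zero only if f = 0 or the mean AHI change is zero.

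**False-positive rate.** Simulated two-sided 5% Pearson test, n = 35, no association among switchers:

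| Switching | r from formula (shift -0.5 SD) | Rejects, -0.3 SD | Rejects, -0.5 SD | Rejects, -0.8 SD | Switchers only |
|---|---|---|---|---|---|
| 90% | -0.07 | 5% | 6% | 10% | about 5% |
| 80% | -0.12 | 7% | 11% | 21% | about 5% |
| 60% | -0.21 | 15% | 26% | 49% | about 5% |
| 50% | -0.24 | 21% | 36% | 60% | about 5% |

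Repeat runs agreed within about 3 points; the 36% cell ranged from 34% to 37%.

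**Sensitivity to the assumptions** (shift of 0.5 SD; f = 10%, 20%, 30%, 40%, 50%):

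- N = 30, airway CV 0.5: 5.0%, 9.8%, 18.3%, 27.3%, 36.8%.
- N = 30, airway CV 1: 5.7%, 8.3%, 13.4%, 19.8%, 27.6%.
- N = 40, airway CV 0.5: 5.9%, 12.9%, 23.5%, 34.6%, 43.8%.

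**Zero mean AHI change.** The average r is zero, so there is no systematic bias. The test is still off its nominal level: 2.7% to 5.9% for f up to 40%, and 9.6% at f = 50% (N = 30, CV 0.5).

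**The case against.** **The text may not put these subjects at (0,0).** The copying rule in 3.3 is written for analyses that compare the two settings and does not name the correlation. Change is not defined in 6.2. A device-off airway is recorded at Visit 1 (3.3), and prior sleep studies are reviewed at screening (5.1), so change from an untreated baseline is conceivable; no subject would then be forced to the origin. This stands as an ambiguity. Test minus standard is still the plainer reading: 6.2 ties the changes to those two settings, 3.3 places AHI and ODI measurement at Visit 2, and no device-off period is described for that night.

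**No change of setting does mean no change in AHI.** True, but by definition rather than by observation. Such a point cannot show whether a larger airway gain brings a larger AHI fall.

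**The inflation may be small.** This stands. Section 3.3 lists five configurations; if each were equally likely to be best, which nothing in the documents supports, 4/5 = 80% would switch and the rate at -0.5 SD would be 11%. At 90% switching it is about 6%. The rates of 49% and 60% need 50% to 60% switching together with a 0.8 SD shift.

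**A reader might infer that the error always favours the hypothesis.** It does not. The pull follows the sign of the switchers' mean AHI change. If the test setting were worse on average, r would be pushed positive and could hide a true negative association.

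**A reader might also infer that every airway change is positive by construction.** That holds only for the measure that selects the setting. Section 3.3 lists three dimensions in two regions and does not say which one defines the largest airway; the others could fall.

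**Conclusion.** The concern holds in a limited form. On the test-minus-standard reading, the Pearson test in 6.2 mixes a spike at (0,0) with the switchers' data, and it can reject with no association among switchers whenever their mean AHI or ODI change is not zero. In the central scenario the false-positive rate runs from about 6% at 90% switching to about 36% at 50%. It becomes material once roughly 20% to 30% of subjects keep the standard setting. The switching share, airway spread and AHI shift are all assumptions.

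It would be tempting to conclude that the artefact could make the trial declare awake endoscopy efficacious. The documents do not support that: 3.4.1 and 5.5 judge usefulness and efficacy only on the reduction in AHI and ODI, not on the correlation. This is a secondary objective in a self-described pilot, so the point is a should-fix. It still bears on what the study may claim about airway size as a guide to configuration, and nothing else in the plan cures it.

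**What to change.** In 6.2:

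1. Define change as test minus standard, for airway size, AHI and ODI.
2. Make the main analysis of every airway-AHI and airway-ODI Pearson correlation the subjects with two different configurations recorded at Visit 2. State that values copied under 3.3 do not enter. Two regions by two outcomes already gives four correlations, and the rule should cover them all.
3. Report the number of switchers beside each r and its confidence interval.
4. Show the all-subject correlation only as a sensitivity analysis.

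This should be settled before the data are analysed, because a subset chosen after seeing the results would carry little weight. It needs no new visit, procedure or data.

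The cost is precision. At 60% switching, n falls from 35 to 0.6 x 35 = 21. By Fisher's z, the correlation detectable with 80% power is tanh(2.802/sqrt(n - 3)): tanh(2.802/sqrt(32)) = 0.46 with 35 subjects and tanh(2.802/sqrt(18)) = 0.58 with 21. The wider interval reflects the information actually collected, since the dropped points carry none on this relation.
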